2 BACKGROUND AND RATIONALE

[figure not shown]
2.1 Background

Allergic rhinitis (AR) is an upper airway inflammatory disease, characterized by symptoms of rhinorrhea, sneezing, and nasal congestion. Although AR is often considered a benign condition, it greatly impacts the quality of life of affected individuals, with economic costs estimated at \$5.3 billion per year in the USA (1,2). World-wide prevalence of AR is estimated at 9% to 42% (3,4). A variety of treatment approaches exist, including anti-histamines, corticosteroids, and immunotherapies, but have associated side effects and variable responses that warrant alternative options that exhibit improved safety and efficacy profiles. None of the current anti-allergic and anti-inflammatory interventions is designed to address a microbiome based approach to restore colonization of a human commensal bacteria to the nasal microbiome to regulate its anti-inflammatory and anti-infective properties. Intranasal administration of ammonia oxidizing bacteria maybe beneficial for the treatment of a variety of local and systemic indications through its anti-inflammatory and anti-infective properties. The objective of this study is to evaluate the safety of intranasally delivered ammonia oxidizing bacteria (AOB) in healthy volunteers and subsequently to evaluate preliminary efficacy of AOB as a prophylaxis treatment in response to a ragweed pollen nasal allergen challenge (NAC) in subjects with a history of seasonal allergic rhinitis (SAR).

Ammonia oxidizing bacteria are essential for the initial step in environmental nitrification processes, specifically the oxidation of ammonia (NH_3) to nitrite (NO_2^-). *Nitrosomonas* are Gram-negative chemolithoautotrophic betaproteobacteria that obtain energy solely from NH_3 oxidation, while fixing CO_2 for their carbon needs (5). Oxidation of NH_3 proceeds in two steps (

[Figure 1](#)) leading to sequential generation of hydroxylamine (NH_2OH) and NO_2^- that require two enzyme complexes: the membrane-bound ammonia monooxygenase (AMO) comprised of subunits AmoA, AmoB and AmoC; and the periplasmic NH_2OH oxidoreductase (HAO). In addition to high NO_2^- levels, NH_3 oxidation leads to nitric oxide (NO) and N_2O production through two independent pathways downstream of NH_2OH production: nitrifier denitrification and NH_2OH oxidation (6).

Figure 1 Nitrifier Denitrification Pathway

B244 is a purified a strain of *Nitrosomonas eutropha* originally isolated from soil samples. Sequencing of the B244 genome revealed a distinct genetic profile from that of other published *Nitrosomonas* strains and AOB genomes. Based on *in vitro* co-culture studies, B244 was able to reduce survival of pathogenic bacteria. Nitrite generation from ammonia concurrently with medium acidification by B244 led to strong antibacterial effects and a marked reduction (~100-fold) in viable counts of methicillin-resistant *Staphylococcus aureus* and *Pseudomonas aeruginosa*, two pathogens frequently isolated from infected skin and wound sites. In contrast, control cultures with B244 in the absence of ammonium or with heat-killed B244 supplemented with ammonium, had no antibacterial effects. The unique metabolic and antimicrobial activity of *Nitrosomonas*, in combination with their lack of virulence render these bacteria as attractive candidates for topical delivery of nitrite and nitric oxide on human skin with potential to improve health in both normal and abnormal skin conditions or wound sites. NO-releasing drugs or NO donors have also shown activity against *Propionibacterium acnes* and other pathogenic bacteria, anti-inflammatory activity, and inhibition of lipogenesis by insulin-stimulated immortal sebocytes (7-9).

To date, there have been no reported infections or health risks associated with topical application or ingestion of *Nitrosomonas* species. The absence of any illnesses attributed to these bacteria despite our widespread exposure indicates that they pose a minimal health risk, if any at all. Infection or tissue damage by *Nitrosomonas* is unlikely, because the sequenced genomes of several *Nitrosomonas* and other AOB lack genes encoding cytotoxins, or other known bacterial virulence factors. Further, AOB are slow growing, as compared to most heterotrophic bacteria, with optimum doubling times of 8 hours or higher. In particular, *Nitrosomonas* growth is rate limited by the availability of ammonia requiring the oxidation of 27 moles NH₃/mole CO₂ fixed. Due to their dependence on ammonia for their growth, the numbers of *Nitrosomonas* on the skin will be necessarily limited and naturally regulated by the amount of ammonia produced in sweat. This would ensure that the amount of nitrite and NO generated would be relatively low, without any adverse effects.

Currently, *Nitrosomonas eutropha* D23 in buffer at a concentration of 1x10⁹ cells/mL is available as a cosmetic product for topical application of a natural source of AOB and NO/NO₂ to improve the appearance of human skin. AOBiome plans to study *Nitrosomonas eutropha* D23 diluted in storage solution (50 mM Na₂HPO₄ and 2 mM MgCl₂, pH 7.6) at defined doses to be provided as an intranasal spray (B244) for therapeutic applications.

B244 is being developed under IND #16487 as a 'live topical' to provide a natural source of AOB and NO/NO₂ to the human skin. Under IND #16487, a phase 1b/2a clinical trial was completed in 2016 where 36 participants with clinical diagnosis of facial acne vulgaris were randomized to receive ascending doses of investigational product (IP) over 14 days. Safety analyses have been completed and there have been no attributable drug related SAEs reported. In addition, a phase 2b/3 clinical trial in 372 patients with clinical diagnosis of facial acne is

currently ongoing. To date, there have been no attributable drug related SAEs reported in this trial.

The proposed clinical study is designed to evaluate the safety of intranasally delivered AOB in healthy volunteers and subsequently to evaluate preliminary efficacy of AOB as a prophylaxis treatment in response to a ragweed pollen nasal allergen challenge in subjects with a history of seasonal allergic rhinitis.

3 OBJECTIVES

3.1 Primary Objective

- To assess the safety and tolerability of B244 relative to vehicle in healthy volunteers during 14 days of treatment and up to 28 days of follow-up. Safety and tolerability will be assessed by reporting of AEs, physical examination and vital signs (blood pressure, heart rate, respiratory rate).

3.2 Secondary Objective(s)

- To evaluate the efficacy of B244 relative to vehicle in treating Total Nasal Symptom Score (TNSS) in subjects with seasonal allergic rhinitis evaluated in a nasal allergen challenge model as a prophylaxis therapy after 14 days of treatment.
- To evaluate the safety and tolerability of B244 relative to vehicle in subjects with allergic rhinitis after 14 days of treatment. Safety and tolerability will be assessed by reporting of AEs, physical examination and vital signs (blood pressure, heart rate, respiratory rate).
- To evaluate the efficacy of B244 relative to vehicle in treating individual nasal symptom scores in subjects with allergic rhinitis evaluated in a nasal allergen challenge model as a prophylaxis therapy after 14 days of treatment.

3.3 Exploratory

- To test the hypothesis that B244 inhibits airway inflammation driven by nasal allergen challenge. The outcome measures will be changes in Peak Nasal Inspiratory Flow, nasal inflammation score using otoscope, intranasal nitric oxide levels and cytokine concentration from nasal cavity pre- and post- nasal allergen challenge in a prophylaxis treatment setting.

4 ENDPOINTS

4.1 Primary

- Safety and tolerability will be assessed by reporting of AEs, physical examination and vital signs (blood pressure, heart rate, respiratory rate) during 14 days of treatment and up to 28 days of follow-up (Part 1).

4.2 Secondary

- Change in TNSS from baseline to 14 days of prophylaxis treatment.
- Change in subjective nasal symptom scores of nasal congestion, rhinorrhea, nasal itching, and sneezing from baseline to 14 days of prophylaxis treatment.
- Nasal symptom-free response rate within each individual symptom scores and percentage of subjects with a 25% or 50% reduction in TNSS after 14 days of prophylaxis treatment.
- Safety and tolerability will be assessed in subjects with allergic rhinitis by reporting of AEs, physical examination and vital signs (blood pressure, heart rate, respiratory rate) during 14 days of treatment (Part 2).

4.3 Exploratory

- Change in Peak Nasal Inspiratory Flow (PNIF), nasal inflammation score using otoscope, intranasal nitric oxide levels, and cytokine concentration in nasal cavity and blood from baseline to 14 days of B244 application and during prophylaxis treatment setting.

5 STUDY DESIGN

- The purpose of this study is to assess the safety and tolerability of B244 relative to Vehicle in healthy volunteers and to evaluate the preliminary efficacy of B244 relative to Vehicle in subjects with seasonal allergic rhinitis.
- This is a Prospective, Controlled, Double Blinded, Multi-Center, Randomized, 3 Arm, Parallel Assignment, Phase 1b/2a Study to assess the safety, tolerability, and preliminary efficacy of B244 delivered as an intranasal spray in healthy volunteers and subjects with seasonal allergic rhinitis. This will be a 2-part study.
 - In Part 1, safety and tolerability will be evaluated during 14 days of study treatment twice-a-day followed by 4 weeks of follow-up in healthy volunteers.
 - In Part 2, preliminary efficacy will be evaluated in subjects with a history of seasonal allergic rhinitis outside of the local pollen season.
- Subjects will be recruited to participate and randomized 1:1:1 to the following interventions:
 1. B244 (140ul per nostril; OD 0.5; 1×10^9 cells/ml) twice-a-day for 14 days
 2. B244 (140ul per nostril; OD 2.0; 4×10^9 cells/ml) twice-a-day for 14 days
 3. Vehicle (140ul per nostril) twice-a-day for 14 days

- ☒ Part 1 (safety and tolerability evaluation in healthy volunteers) will enroll 24 subjects. Up to 12 subjects per dose cohort (n=8 active, n=4 vehicle) will be enrolled, with a target of 20 subjects completed (10 subjects per dose cohort; n=7 active, n=3 vehicle) assuming a 16.7% drop out rate.
- ☒ Safety and tolerability will be assessed by reporting of AEs, physical examination and vital signs (blood pressure, heart rate, respiratory rate) during 14 days of treatment and up to 28 days of follow-up.

- ☒ An internal safety committee meeting will review the 2 week Part 1 safety data and, if there are no safety concerns, the study will proceed to Part 2 to evaluate preliminary efficacy in subjects with a history of seasonal allergic rhinitis (SAR).

- Part 2 (preliminary efficacy evaluation in subjects with a history of SAR to ragweed pollen) will enroll 42 subjects. Up to 14 subjects per arm (1×10^9 cells/ml; 4×10^9 cells/ml or vehicle) will be enrolled, with a target of 12 subjects per arm for a total of 36 subjects completed, assuming a 10-15% drop-out rate.
- Safety and tolerability will be assessed in subjects with allergic rhinitis by reporting of AEs, physical examination and vital signs (blood pressure, heart rate, respiratory rate) during 14 days of treatment.
- A preliminary efficacy assessment will be performed in response to nasal allergen challenge (NAC) in a prophylaxis treatment setting.
- Subjects will be asked to report for a screening visit (Visit 1) and if all inclusion/exclusion criteria are met, subjects will be asked to report for a NAC titration (ragweed pollen nasal allergen titration) visit to administer a single provocative challenge dose for each subject (Visit 2). Subjects will then return 14 days after the washout period for basic health checks and baseline assessments (intranasal fluid, TNSS, PNIF, intranasal nitric oxide, and have a nasal inflammation score) followed by confirmatory NAC (NAC#1) (Visit 3). During this time subjects will use a study diary to complete TNSS at -30 (30 minutes prior to NAC), 0 (baseline prior to NAC), 15, 30, 45, 60, 90, and 120 minutes. PNIF at -30, 0, 15, 30, 60, and 120 minutes will also be obtained. TNSS is the sum of four individual symptom scores (running nose, congestion, itchy nose, and sneezing) rated on a four point scale (0-3). Subjects are required to meet the minimum qualifying TNSS score of a change of 6/12 from their baseline score, on at least 2 diary cards. Subjects will also provide samples for intranasal fluid at 0, 20, and 60 minutes, measure intranasal nitric oxide (nNO) and have a nasal inflammation score assessed by the investigator using a nasal otoscope at 0 and 120 minutes, in addition to blood collection at 120 min for biomarkers. Subjects meeting the requirement will be randomized to one of the three treatment arms. Randomization will be 1:1:1 so that equal number of subjects will be treated in each arm of the study. Subjects will then be trained on the use of the nasal spray, and have their first dose of treatment on site (self-dosing). Subjects will remain onsite for observation for 1 hour post dosing. Subjects will then be dispensed study medication for 14 days of at home dosing. While at home, subjects will dose twice daily (am and pm), and record their dosing, and any occurrence of an AE and TNSS using a study diary.
- Subjects will return to the clinic for the last dose following the 14 days of at home dosing for their final visit (Visit 4). During this time subjects will again have their baseline assessments and be exposed to ragweed pollen challenge (NAC#2), and will use a study diary to complete TNSS at -30, 0, 15, 30, 45, 60, 90, and 120 minutes and PNIF at -30, 0, 15, 30, 60, and 120 minutes. Prior to and 20 and 120 minutes after NAC #2, subjects will additionally provide samples for intranasal fluid, and have nNO measured and have a nasal inflammation score assessed by the investigator using a nasal otoscope at 0 and 120 min, in addition to blood collection at 120 min for biomarkers.

- For Part 2, study will be paused for safety review using the same stopping criteria as in Part 1.
- Rescue medications will not be allowed during the study.

6 SELECTION OF STUDY PARTICIPANTS

6.1 Study Population

Normal healthy volunteers and subjects with a history of seasonal allergic rhinitis to ragweed pollen are eligible for enrollment. Patients must be willing to refrain from using any treatments, investigational products, including herbal medicines while participating in this study.

6.2 Number of Participants Planned

Part 1 (safety and tolerability evaluation in healthy volunteers) will enroll 24 subjects. Up to 12 subjects per dose cohort (n=8 active, n=4 vehicle) will be enrolled, with a target of 20 subjects completed (10 subjects per dose cohort; n=7 active, n=3 vehicle) assuming a 16.7% drop out rate.

Part 2 (preliminary efficacy evaluation in subjects with a history of SAR to ragweed pollen) will enroll 42 subjects. Up to 14 subjects per arm (1×10^9 cells/ml; 4×10^9 cells/ml or vehicle) will be enrolled, with a target of 12 subjects per arm for a total of 36 subjects completed, assuming a 10-15% drop-out rate.

6.3 Inclusion Criteria

- Males and Females, 18 to 65 years of age (committed to consistent use of an acceptable method of birth control as described in Section 10).
- In good general health as determined by a thorough medical history and physical examination, and vital signs.
- Nonsmoker or ex-smoker (stopped >1 year prior to study entry).
- Subjects willing and able to provide written informed consent.
- Is willing and able to comply with the requirements of the protocol and must be available for the full duration of the study.
- For Part 1, subjects asymptomatic from any seasonal or perennial allergens.
- For Part 1, elevated systolic blood pressure greater than 120 but less than 160 and never been on antihypertensive medications or have been off any hypertensive treatment for a period of 12 weeks or longer.
- For Part 2, subjects with a well-documented history of seasonal allergic rhinitis (specifically ragweed pollen) with documentation of sensitivity by positive skin testing and/or IgE testing to the relevant allergens 12 months prior to enrollment that correlate with clinical history.

- For Part 2, a ragweed positive skin prick test with a wheal diameter at least 5 mm larger than the negative control and/or a ragweed specific IgE greater or equal to 0.7 kU/L.
- For Part 2, subjects with confounding allergies, or sensitization to cat epithelia, dog epithelia, *Dermatophagoides farinae*, or *Dermatophagoides pteronyssinus* or prevalent and relevant seasonal allergens as per the skin prick test may be included if sensitization is not clinically relevant (ie. subject is non-symptomatic and/or can avoid the allergen during the study) at the discretion of the Investigator.
- For Part 2, subjects with a baseline TNSS at Visit 3 and a minimum qualifying TNSS score of a change of 6/12 from their baseline score after NAC #1 on at least 2 diary cards.
- For Part 2, subjects' average post diluents nasal congestion score must be 1 at admission for each study visit.

6.4 Exclusion Criteria

Deviations from exclusion criteria are not allowed because they can potentially jeopardize the scientific integrity of the study, regulatory acceptability or participant safety. Therefore, adherence to the criteria as specified in the protocol is essential

Patients who meet any of these criteria are not eligible for enrollment as study participants:

- Pregnancy or breast-feeding
- Female of childbearing potential not using adequate contraceptive measures.
- Smoking within the past year or during the protocol.
- Systemic corticosteroid or other immunosuppressive medications use in the previous three months or during the protocol.*
- Intranasal corticosteroid use in the previous month or during the protocol.*
- Intranasal antihistamine or cromolyn use in the previous week or during the study.*
- Allergen immunotherapy during previous 12 months or during the protocol.*
- Omalizumab use in previous 12 months or during the protocol.*
- Systemic antihistamine or leukotriene modifying medication use in the previous week or during the protocol.*
- Use of antibiotics, NSAIDS, antihypertensives, beta-blockers, photosensitizing medications, or vitamin D supplements during study. Antihypertensive and beta-blocker exclusion applies to Part 1 only.
- Use of any intranasally administered over-the-counter product or nasal irrigation (e.g., neti pot) during study.
- Inability to give informed consent.
- Persistent asthma or any medical condition that in the opinion of the investigator may compromise the subject's ability to safely participate in the study.

- Subjects with any significant clinical abnormalities which may interfere with study participation.
- Prior use of AO+ Mist.
- Subjects with immunodeficiencies, nasal lesions, nasal polyps, or sinus infections.
- Use of an investigational drug within 30 days before screening Visit 1.

* Exclusionary criterion due to 1) medication use as marker of persistent comorbid allergic or inflammatory condition that may increase subject risk with study participation, 2) potential of medication to interfere with study outcome measures or results.

7 PARTICIPANT ENROLLMENT

7.1 Consenting Participants

Informed consent for participation in the study must be obtained before performing any study-specific procedures.

Informed Consent Forms for enrolled participants and for participants who are not subsequently enrolled will be maintained at the study sites in secure study files. Consent will be obtained by trained research study staff trained in taking informed consent. The study will be explained with the opportunity for the participant to ask questions. If a participant wishes to enter the study, a consent form will be completed and signed.

7.2 Screening for Eligibility

For Part 1, after informed consent has been obtained, screening assessments (Visit 1) will be performed within 3 weeks (-21 days to 0) prior to the Baseline visit (Visit 2) to determine participant eligibility for enrollment in the study. All screening evaluations must be completed and reviewed to confirm that participants meet all eligibility criteria before randomization on Day 0 (Visit 2). Inclusion and exclusion criteria will be reviewed at Screening (Visit 1) and Baseline visit (Visit 2) to make sure nothing changed. The participant's medical history and medication use will be reviewed. A brief physical examination including height, weight, vital signs, nasal inspection, and 12-lead ECG will be performed. Laboratory testing, including blood sample for a comprehensive metabolic panel, complete blood count, chemistry, lipid panel, and liver function test, as well as urinalysis, will also be performed as part of screening. Urine pregnancy test will be performed on WOCBP.

For Part 2, after informed consent has been obtained, screening assessments (Visit 1) will be performed within 3 weeks (-21 days to 0) prior to the NAC titration (Visit 2) and NAC #1 (Visit 3) visits to determine participant eligibility for enrollment in the study. All screening evaluations must be completed and reviewed to confirm that participants meet all eligibility criteria before randomization on Day 14 (Visit 3). Inclusion and exclusion criteria will be reviewed at Screening (Visit 1). The participant's medical history and medication use will be reviewed. A

brief physical examination including height, weight, vital signs, and nasal inspection, will be performed. Laboratory testing, including blood sample for a comprehensive metabolic panel, complete blood count, chemistry, lipid panel, and liver function test, as well as urinalysis, will also be performed as part of screening. Urine pregnancy test will be performed on WOCBP. Additionally, ragweed pollen allergen skin test (skin prick test) and/or blood collection for ragweed pollen specific IgE will be performed as part of screening if documentation of a positive test within the past 12 months for either method cannot be provided.

All screening assessments are listed in the Schedule of Events Table (Appendix A). A participant must meet all inclusion criteria, and none of the exclusion criteria, to be enrolled and randomized in this study. The Investigator and team will maintain a screening log to record details of all persons screened and to confirm eligibility or record reasons for screening failure, as applicable.

7.3 Study Withdrawal and Withdrawal from Investigational Product and Stopping Criteria

A participant may withdraw from the study at any time at his/her own request, or may be withdrawn at any time at the discretion of the Investigator.

Reasons for withdrawal (participants who refuse to complete any remaining study visits) or discontinuation (participants who prematurely stop the application) at any time during the study may include, but are not limited, to the following:

- For safety reasons, either at the discretion of the Investigator or at the participant's request
- For protocol violations at the discretion of AOBiome
- Due to concomitant therapy that could interfere with the results of the study (the Investigator will report all such information on the CRFs and decide, in accordance with AOBiome, whether the participant is to be withdrawn).

The reason for participant study withdrawal will be recorded in the electronic Case Report Form (eCRF). Data from participants withdrawing from the study will be considered evaluable up to the point at which they are withdrawn using the same criteria for evaluability as for participants who complete the study.

For Part 1 safety evaluation and Part 2 preliminary efficacy , AOBiome will include study stopping rules to pause study for safety review in the event that ~~t1~~ subject reports a SAE, ~~t2~~ grade 3 (severe) AEs, or ~~t3~~ grade 2 (moderate) AEs considered possibly, probably, or definitely related to the investigational product.

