7.5 Early Termination

Participants who have discontinued the study early will be evaluated by the Investigator at the Unanticipated Visit. See the list of assessments to be performed at the Unanticipated Visit in the Schedule of Events Table (Appendix A). Participants with ongoing AEs or SAEs believed to be possibly related to investigational product (IP) will continue to be followed until resolution or for 30 days as warranted by the nature of the AE.

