14.2 Populations for Analysis

ITT: includes all randomized participants.

Safety: includes all subjects who received at least 1 dose of study medication.

Per Protocol: subjects who administered at least 50 % of IP, have at least one baseline and post baseline in clinic visit and did not have any major protocol violations.

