14.5.1 Handling of Dropouts or Missing Data

Missing data will not be imputed for analysis.

Subjects who dropout after enrollment but prior to randomization will be replaced.

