## **2.2. Study Populations**

### Intent-to-Treat Population

All randomized patients will be included in the Intent-to-Treat Population.

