### Per Protocol Population

All subjects who administered at least 50% of study medication by weight, have at least one baseline and post baseline in clinic visit and did not have any major protocol violations will be included in the per protocol population.

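### Randomised Part 2 subjects can be taken out of the study for protocol violations at the sponsor's discretion, so their Visit 4 outcome can be missing from the ITT comparison

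*Protocol*

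**What the plan says.** Protocol 7.3 opens its list with "Reasons for withdrawal (participants who refuse to complete any remaining study visits) or discontinuation (participants who prematurely stop the application", and one item in it is "For protocol violations at the discretion of AOBiome". Section 12.6 repeats the item. Neither section defines which violations count, who reviews them or when. Neither confines the ground to the period before randomisation.

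For those who leave, 7.3 states "Data from participants withdrawing from the study will be considered evaluable up to the point at which they are withdrawn". Section 7.5 adds "Participants who have discontinued the study early will be evaluated by the Investigator at the Unanticipated Visit". The procedures for that visit in 10.6.5 include no allergen challenge.

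On analysis, Protocol 14.2 has "ITT: includes all randomized participants" and SAP 2.2 has "All randomized patients will be included in the Intent-to-Treat Population". Protocol 14.5.1 says "Missing data will not be imputed for analysis", and only dropouts before randomisation are replaced. SAP 2.8 covers what listings display and the imputation of partial dates. It gives no method for a missing outcome. SAP 2.5.1 tests TNSS and its area under the curve by ANCOVA at Visit 4, with the Visit 3 value as covariate.

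Violators are already dealt with elsewhere. In the SAP, subjects who meet the use and visit conditions and "did not have any major protocol violations will be included in the per protocol population". Protocol 14.2 has the same exclusion.

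**The concern.** An all-randomised analysis protects the comparison only if outcomes are sought from everyone randomised. A discretionary exit after randomisation weakens that protection, because violations such as missed doses or use of other medication can follow from symptoms or poor tolerability. If they do, the subjects removed differ from those who stay, and they may differ by arm. The observed Visit 4 difference then partly reflects who was left to be challenged.

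No analytic need calls for the removal. SAP 4.1 plans separate ITT and per-protocol TNSS tables, and Protocol 14.6 summarises deviations in all randomised patients. Keeping violators in follow-up serves both analyses. Taking them out of the study moves the ITT result towards the per-protocol one.

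**Working it through.** 1. **The plan's own numbers (Protocol 14.1, SAP 2.7).** Enrolment = completers / (1 − dropout).
   - Part 1: 20 / (1 − 0.167) = 24.01, against 24 planned.
   - Part 2: 36 / 0.90 = 40.0 and 36 / 0.85 = 42.4, against 42 planned. The implied dropout is 1 − 36/42 = 14.3%.
   - These reproduce. In Part 2 each arm has 14 − 12 = 2 subjects to spare for losses of every kind.

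2. **One subject followed through the text.** Take a Part 2 subject randomised at Visit 3 and taken out of the study for a violation before Visit 4.
   - Data up to that point are kept (7.3).
   - The exit assessment has no challenge (7.5, 10.6.5), so there is no NAC #2 TNSS.
   - The gap is not filled (14.5.1), and the subject is not replaced.
   - The subject is in the ITT set by definition but has no Visit 4 value, so contributes nothing to the ANCOVA.
   - No section asks a subject who has been withdrawn, or who has only stopped the spray, to return for NAC #2.

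3. **Share of an arm.** One loss is 1/14 = 7.1%. If the two planned losses also occur, one more leaves 11 (3/14 = 21.4% lost) and two more leave 10 (4/14 = 28.6% lost), against a planned 10-15%.

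4. **Possible shift in a mean.** With m of n subjects removed from one arm, observed mean − full mean = (m/n) × (retained mean − removed mean). The documents give no value for the bracket, so I assume a range of 1, 2, 4 and 6 points on the 12-point scale.
   - m = 1: 0.07, 0.14, 0.29, 0.43 points.
   - m = 2: 0.14, 0.29, 0.57, 0.86 points.
   - If the other arm loses nobody, the between-arm difference shifts by the same amount.

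5. **Possible range for a responder rate (25% or 50% reduction).** Setting the missing results to all failures and then to all successes leaves the rate undetermined over m/14. For m = 2 that is 14.3 percentage points in an arm, and 28.6 points for a difference if both arms lose two. This holds for any two missing subjects, whatever the reason.

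6. **Precision.** Unadjusted standardised difference detectable with 80% power = (1.645 + 0.842) × √(2/n). The one-sided 0.05 level is my assumption; Protocol section 13 says one-sided but gives no level. The result is 0.94 at n = 14, 1.02 at 12 and 1.11 at 10. SAP 2.7 says the sample size has no statistical basis, so no planned power is lost.

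**The case against.** The case for leaving the text alone has real weight.

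- **The item may mean only stopping the spray.** The list covers both withdrawal and discontinuation, and 7.3 describes withdrawal as the participant's own refusal of further visits, which a sponsor decision is not. The list is also permissive. This stands: a reader might infer that every violator will be taken out of the study, and the text does not say so. It does not say the opposite either, and that ambiguity is a reason to amend.
- **Sponsor staff are blinded** (Protocol 8.4), and SAP 2.6 unblinds each part only after its lock. This limits deliberate selection. It does not help if violations themselves differ by arm through tolerability. The section 8.1 table also describes the active product as cloudy and light pink and the vehicle as clear and colourless, though in identical white bottles.
- **The window is short.** Part 2 schedules no visit between Visit 3 (Day 14) and Visit 4 (Day 28). Bottles are weighed at those two visits, so poor adherence by weight surfaces only at the outcome visit. This stands. Earlier removal remains possible for violations that come to light in another way.
- **Safety follow-up is not abandoned.** A reader might infer that the Part 1 primary endpoint is compromised. The documents do not support that. It is summarised descriptively in everyone dosed (14.4.1), and data before withdrawal count. Early leavers are assessed for vital signs, laboratory tests and adverse events (10.6.5). Section 12.6 asks for full evaluation when possible, serious events are followed to recovery or stabilisation (15.7), and Part 1 has a 180-day contact (12.2). How many of the Day 14, 21 and 42 visits are lost depends on when the subject leaves.

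**Conclusion.** The point holds for Part 2 efficacy. The text permits a discretionary exit after randomisation that can remove the Visit 4 outcome from an analysis described as all-randomised, when the per-protocol set already handles violators. Each case costs 7.1% of an arm. Two cases in one arm would shift its mean by 0.14 to 0.86 TNSS points under the assumed differences of 1 to 6 points.

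These are ranges, not estimates: the documents give no expected number of such removals, and there may be none. A reader might conclude that the ITT analysis becomes a per-protocol analysis and that no unselected comparison is left. That would require removal to be routine and to happen before Visit 4, and the documents show neither. Part 2 efficacy is secondary and preliminary. This is a cheap improvement that should be made; it does not invalidate the design.

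**What to change.** In Protocol 7.3 and 12.6:

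- Separate stopping the product from leaving the study, and say which of the two each listed reason leads to.
- Remove protocol violation as a sponsor-discretion ground for leaving the study after randomisation.
- State that a randomised subject with a violation continues scheduled follow-up and outcome collection, including Visit 4, subject to consent and the investigator's safety judgement.
- State that violations are recorded and used only to define the per-protocol set, with membership decided before unblinding.

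Reconcile this with two neighbouring texts: the concomitant-therapy ground in 7.3 and 12.6, and section 8.14, which treats a subject who needs rescue medication as an early termination. Unless these are aligned, prohibited-medication violators could still leave by another route. Which clinical rule should apply there is for the sponsor and investigators to settle. Nothing here changes any rule on stopping treatment.

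The cost is a few sentences in an amendment, a few more visits from non-adherent subjects, and possibly slight dilution of the ITT effect.
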